## Intervention and Outcome Variables

[figure not shown]

Figure 1. Somatosensory intervention plan for preterm infants along with the salivary sampling protocol and digitized measurements of non-nutritive suck progression is shown above. Primary (salivary gene expression), and secondary (transition to full oral feed, oromotor NNS pattern formation, NICHD Neonatal Research Network feeding-growth questionnaire, and Bayley III screener at NICU follow-up) outcome variables are given.

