Official Title: Somatosensory Modulation of Salivary Gene Expression and Oral Feeding in Preterm Infants

NCT number: NCT02696343

Document Date: 3-31-24

Statistical Analysis Plan.

Primary Outcome: Gene Expression

In this randomized controlled clinical trial, we analyzed salivary developmental gene expression changes in extreme and very preterm infants randomized to receive either therapy with the NTrainer feeding system or a 'Sham' mode (blind pacifier) to assess the effect of therapy on the developing infant. Salivary samples were collected at a series of timepoints, beginning with the initiation of therapy through the learning process of oral feeding or to transfer to an outlying hospital. The primary goal of this study was to assess and compare differences in gene expression patterns over time between groups. The expression of six genes involved in 1.) memory: *CDH13*; oral development: *FOXP2* and *WNT3*; 3.) sensory integration: *NPHP4*, and *PLXAN1*; and hunger signaling: *NPY2R*, along with two reference genes for proper normalization were measured via RT-qPCR for each subject at 6 timepoints. The raw CT values were normalized for each subject and timepoint by subtracting the geometric mean of the reference genes from the mean expression of each gene (deltaCT). These deltaCT values were used for the remainder of the analysis. A positive deltaCT value indicates that the target gene had lower expression than the reference gene; conversely increasing deltaCTs are indicative of decreasing expression. In order to determine changes in gene expression, one way and two-way ANOVA analysis in R [1] was used. Initially, the analysis was done to assess expression pattern changes over time for 1.) the cohort as a whole, 2.) based on treatment status, and 3.) by sex. Given that the timepoint measurements are done on the same subject, repeated measure ANOVA and subject for which all time points were not measured were excluded from the analysis. Subsequently, the analysis was extended by grouping subjects by bronchopulmonary dysplasia (BPD) status, looking at the effect over time, the effect of treatment status and the interaction of the two. BPD was defined based on NIH criteria.

Secondary Outcomes: Non-nutritive Suck Dynamics and Growth in Daily Oral Feeds

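### Six unranked genes form the primary outcome with no alpha, success rule or adjustment; if any one gene counts at an assumed 0.05, the false-positive chance is 26.5% under independence, at most 30%

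*SAP*

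**What the plan says.** The protocol's Figure 1 legend (Intervention and Outcome Variables) divides the outcomes into "Primary (salivary gene expression), and secondary" ones and names no single gene. Its Gene Expression Analysis paragraph lists six target genes. The SAP, under Primary Outcome: Gene Expression, groups the same six by biological function and does not order them.

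The SAP gives the aim as follows: "The primary goal of this study was to assess and compare differences in gene expression patterns over time between groups". The genes "were measured via RT-qPCR for each subject at 6 timepoints", and each value is normalized by "subtracting the geometric mean of the reference genes from the mean expression of each gene (deltaCT").

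On testing, it says that "one way and two-way ANOVA analysis in R [1] was used", and adds that the repeated-measures form applies. The first round of analyses covers "1.) the cohort as a whole, 2.) based on treatment status, and 3.) by sex". The next step is set apart: "Subsequently, the analysis was extended by grouping subjects by bronchopulmonary dysplasia (BPD) status". On missing samples, "subject for which all time points were not measured were excluded from the analysis".

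Neither document states an alpha, a rule for when the primary outcome is met, a composite or global test across genes, or any multiplicity adjustment. The only power statement is in the SAP under Secondary Outcomes, and it gives no alpha either.

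**The concern.** A primary outcome made up of six separate measurements needs a rule that turns six results into one conclusion. Without it, a reader cannot tell whether one nominally significant gene out of six would be reported as an effect of the intervention on gene expression. If it would, the overall false-positive rate is several times the per-gene level over most of the plausible range of correlation.

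The decisive term is not named either. The stated aim points to the treatment-by-time interaction, because it compares patterns over time between groups. But the analysis list places the treatment comparison beside the whole-cohort and sex analyses with no ranking. At stake is whether a positive finding on the primary outcome can be told apart from a chance result.

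**Working it through.** **Inputs from the documents.** Six target genes (both documents). Six timepoints per gene and two arms (SAP, Primary Outcome). For power only: f = 0.10, correlation 0.60 among repeated measures, 80% power at 110, final sample 114 (SAP, Secondary Outcomes).

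**Assumptions.** Alpha of 0.05 per gene; one treatment-by-time test per gene, with (2 − 1) × (6 − 1) = 5 degrees of freedom; any one significant gene counts as success; equal pairwise correlation r between genes. The documents give none of these four.

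**Step 1: the plan's own figure.** Repeated-measures ANOVA, noncentral F, with λ = f² × N × m / (1 − ρ), df1 = m − 1 and df2 = (N − 2)(m − 1).
- With m = 4 and N = 110: λ = 0.01 × 110 × 4 / 0.40 = 11.0, df 3 and 324, power 79.9% at alpha 0.05. This matches the stated 80%.
- With m = 6 and N = 110: λ = 16.5, df 5 and 540, power 89.7%. This does not match.

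So the SAP's figure fits four measures and a single test at 0.05. Four is an inference; it equals the number of intervention phases listed for the secondary analyses. The calculation does not appear to have been made for the six-timepoint gene analysis.

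**Step 2: chance of at least one false-positive gene, all nulls true.**
- Independent tests: 1 − 0.95⁶ = 26.5%.
- Ceiling under any dependence: 6 × 0.05 = 30%.
- Other assumed per-gene levels, independent, 1 − (1 − α)⁶: 5.9% at 0.01, 14.1% at 0.025, 46.9% at 0.10.
- Correlated tests, by simulation of six equicorrelated 5-df chi-square statistics. The last column uses 0.05/6, the first Holm step, which sets the family-wise error when every null holds:

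| r | each gene at 0.05 | Holm at 0.05 |
|---|---|---|
| 0 | 26.5% | 4.9% |
| 0.3 | 24.6% | 4.7% |
| 0.5 | 21.7% | 4.3% |
| 0.7 | 17.4% | 3.6% |
| 0.8 | 14.8% | 3.0% |
| 0.9 | about 11% | about 2% |

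A simulation of the repeated-measures F test itself (two arms, six times, N = 114, compound symmetry) gave 26.6%, 24.4%, 21.5%, 17.0% and 14.8% at r = 0, 0.3, 0.5, 0.7 and 0.8. Some positive correlation is plausible, because every gene's value subtracts the same reference-gene mean from the same sample. Its size is unknown.

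**Step 3: power cost of the strictest Holm step (0.05/6 = 0.0083).** Same formula, f = 0.10, ρ = 0.60, sphericity assumed:

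| measures | N | λ | power at 0.05 | power at 0.0083 |
|---|---|---|---|---|
| 4 | 114 | 11.4 | 81% | 59% |
| 6 | 114 | 17.1 | 91% | 75% |
| 6 | 80 (assumed completers) | 12.0 | 76% | 52% |
| 6 | 60 (assumed completers) | 9.0 | 61% | 35% |

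If sphericity fails, λ and both degrees of freedom are multiplied by ε. With six measures and N = 114, power falls from 85% to 65% at ε = 0.8 and from 77% to 52% at ε = 0.6.

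These power figures are illustrations. The SAP states f = 0.10 for an effect over time in the secondary outcomes, not for a treatment-by-time effect on a gene.

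**The case against.** **The percentage belongs to one reading of the plan.** It needs an any-gene rule that neither document states. If all six genes had to show an effect, the false-positive chance could not exceed the per-gene level. This stands, and the figure must be read conditionally. It does not rescue the plan, which states no all-six rule.

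**The genes may be strongly correlated.** This also stands in part. A narrow band such as 15% to 25% would rest on choosing correlations of about 0.3 to 0.8. At 0.9 the figure is about 11%, and at 0.95 about 9%. Only 26.5% and the 30% ceiling need no assumed correlation value beyond independence or none at all. Even so, every value shown exceeds 5%.

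**The work is exploratory.** The SAP describes a randomized controlled trial with a declared primary outcome and a primary goal. If exploratory intent was meant, it needs to say so.

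**A reader might infer a much larger problem** by counting the whole-cohort, treatment and sex analyses of every gene: 18 independent tests at 0.05 give 1 − 0.95¹⁸ = 60%. The documents do not support this as the error rate of the primary outcome. The stated aim is a comparison between groups over time, which the whole-cohort and sex analyses do not address, and BPD is presented as a later extension.

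**Holm is not the only remedy.** True. A single multivariate test, a fixed testing order or an explicit all-genes rule would also define the error rate.

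**Conclusion.** The omission is certain: six unranked genes, with no alpha, success rule or adjustment. The error rate of the primary analysis is therefore undefined.

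If any one gene counts and each is tested once at an assumed 0.05, the chance of at least one false-positive gene is 26.5% under independence and at most 30% under any dependence. It falls as the unknown correlation between genes rises, to 14.8% at 0.8 and about 11% at 0.9.

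It would be tempting to say that this trial runs a false-positive risk of about one in four, or that a reported gene effect is spurious. The documents support neither statement. The first depends on a rule and an alpha that are not written down, and the second on results that are not given. The plan should be changed because, followed as written, it lets any one of six nominal results be read as a primary effect.

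**What to change.** 1. Name the treatment-by-time interaction as the single primary test for each gene, in line with the stated aim.
2. State a family-wise level of 0.05 and apply Holm across the six genes, which is valid under any dependence between them. Report adjusted p-values beside the nominal ones.
3. Label the whole-cohort, sex and BPD analyses of gene expression exploratory.
4. The SAP is written in the past tense. Disclose that these choices were made after the analysis and do not restore prespecified error control.

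**Cost.** No new data are needed, only recalculated p-values, labels and a disclosure. The real price is power per gene, by the amounts in the step 3 table. The plan should not set its 80% at 110 against the gene analysis, because that figure reproduces with four measures rather than six. Complete-case exclusion lowers power further; the number of infants with all six samples is not stated and should be reported.

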A-priori power calculation indicated that a sample size of 110 was required for 80% power, with an assumed correlation of 0.60 among repeated measures and a small effect over time (Cohen's $f = 0.10$). This effect was considerably smaller than those observed in our previous empirical data ($f = 0.22-0.24$), suggesting adequate power for the final sample of 114 neonates in this study.

Linear mixed modeling (LMM) analysis was performed for non-nutritive suck (NNS) variables including NNS Bursts/minute, NNS Suck Cycles/minute, NNS Amplitude, NNS Spatiotemporal Index, and the transition to independent oral feeds based on daily measures of percent oral intake (%PO) to examine the effects of GA, PMA, sex (male, female), respiratory diagnosis (non-BPD, BPD), treatment (NTrainer, Sham), intervention phase (0, baseline), (1, low-dose), (2, high-dose), (3, post intervention), and potential interactions. The models

accounted for nesting of repeated measurements within infants (i.e., intraclass correlation), and a proper error covariance structure was determined based on model fit (i.e., adjusted Akaike Information Criterion, Bayesian Information Criterion). In addition, locally estimated scatterplot smoothing (LOESS) analysis was conducted to estimate the trajectory of %PO growth over PMA. All statistical analyses were conducted using R [1] and SAS 9.4 [2].

References

1. R Core Team. R: A language and environment for statistical computing. R Foundation for Statistical Computing (2019) <http://www.R-project.org/>
2. SAS Institute. SAS/STAT 9.4 user's guide. (2002-2012).

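### The primary six-time-point repeated-measures ANOVA has no sphericity check or correction specified; without one, its time and treatment-by-time tests could run at anywhere from about 5% to about 10%, depending on a deltaCT covariance that the documents do not give.

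*SAP*

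**What the plan says.** The SAP, under Primary Outcome: Gene Expression, sets the aim: "The primary goal of this study was to assess and compare differences in gene expression patterns over time between groups". The treatment-by-time comparison is therefore central. The six target genes and the reference genes "were measured via RT-qPCR for each subject at 6 timepoints". The method is "one way and two-way ANOVA analysis in R", and the text then says: "Given that the timepoint measurements are done on the same subject, repeated measure ANOVA". Infants lacking any time point are dropped. The section names no sphericity test, Greenhouse-Geisser or Huynh-Feldt adjustment, multivariate alternative, R function or significance level. It does not say which six samples were analysed or how they were spaced.

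For the suck and oral-feeding outcomes, under Secondary Outcomes, the SAP uses linear mixed models and says that "a proper error covariance structure was determined based on model fit". The primary analysis has no counterpart to this.

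**The concern.** The univariate repeated-measures F test for a within-subject factor is exact only under sphericity: the difference between any two time points must have the same variance for every pair. With six levels this covers 15 pairwise differences. The Protocol (Saliva Collection) has sampling about every three days from baseline until full oral feeds or discharge. In a maturing infant, neighbouring samples may well correlate more than distant ones. If they do, the nominal 5 numerator degrees of freedom, and the matching denominator, are too many, and the test rejects a true null too often.

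The tests at risk are those for change over time and for treatment by time, run for each of six genes. No multiplicity control is stated. If the six tests were independent, the chance of at least one false positive would be 1 - 0.95^6 = 26.5% at a true 5% per test, and 1 - 0.92^6 = 39.4% at a true 8%.

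**Working it through.** **Inputs from the documents.** There are m = 6 time points (SAP, Primary Outcome). The final sample is 114, with a single assumed correlation of 0.60 and f = 0.10 (SAP, Secondary Outcomes). **Assumptions.** Two arms; nominal level 5%; N = 114 as the most complete cases possible and N = 60 as a lower scenario, because the number of infants with all six samples is not given. The covariance of deltaCT is not given either, so a range is shown.

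**The plan's own figure.** The SAP states 110 infants for 80% power. For a within-between interaction with k = 2 groups:

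- λ = f²·N·m·ε/(1 - ρ)
- df = (m - 1)ε and (N - k)(m - 1)ε

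With m = 4 and ε = 1, N = 111 (power at 110 is 79.9%), which matches. With m = 6 and ε = 1, N = 87, which does not. With m = 6 and ε about 0.70-0.74, or m = 5 and ε about 0.80-0.85, N is again about 110. The inputs behind 110 are therefore not unique, and the figure does not reveal what was assumed about sphericity.

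**Departure from sphericity.** Let Σ be the 6×6 covariance of the time points and C a set of five orthonormal contrasts. With A = C′ΣC,

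ε = [tr(A)]² / [5·tr(A²)],

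which lies between 1/5 = 0.20 and 1.

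**Size of the uncorrected test.** Box's approximation is P{F(5ε, 5(N - 2)ε) > F₀.₉₅(5, 5(N - 2))}; for N = 114 the nominal df are 5 and 560. At the bound ε = 0.20 it gives 13.8%. Because it runs somewhat high at low ε (9.65% at ε = 0.50, against 8.5-8.7% simulated), the table uses simulation under the null with 20,000 trials per row.

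| Structure, N = 114 | ε | Time | Treatment × time |
|---|---|---|---|
| Common correlation 0.60 | 1.00 | 5.0% | 4.9% |
| AR(1) 0.3 | 0.90 | 5.5% | 5.5% |
| AR(1) 0.5 | 0.77 | 6.4% | 6.5% |
| AR(1) 0.7 | 0.63 | 7.5% | 7.6% |
| AR(1) 0.79 (average correlation 0.60) | 0.57 | 8.0% | 8.0% |
| AR(1) 0.95 | 0.47 | 8.8% | 9.0% |

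At N = 60 the largest values are 9.2% (time) and 9.7% (treatment by time), both at AR(1) 0.95. A common correlation of 0.60 with the SD rising 1.5- to 3-fold over time gives 5.2-6.7% at N = 114.

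**Adding independent noise.** If a share s of the variance is sampling and assay noise, the correlation at lag d becomes (1 - s)ρ^d, and ε moves towards 1.

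- s = 30%, ρ = 0.5/0.7/0.8/0.9: ε = 0.90/0.85/0.85/0.90; Box size 5.7/6.1/6.1/5.7%; simulated sizes about 5.0-6.5%.
- s = 50%: ε = 0.94-0.97; Box size 5.2-5.4%; simulated sizes about 4.9-5.5%.

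**With a correction.** Across the structures without added noise, Greenhouse-Geisser gives 4.5-4.9% at N = 114 and 4.1-5.1% at N = 60. Huynh-Feldt gives 4.7-5.0% and 4.6-5.4%.

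**The case against.** The strongest reply is that the documents do not establish any inflation. Four parts of it deserve an answer.

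- **The SAP's only correlation is a single 0.60.** Read as common to all pairs with equal variances, it gives ε = 1 and size 5%. That reading is possible, but the figure is a power input under the secondary-outcomes heading, not a covariance model for deltaCT. An AR(1) pattern with the same average correlation gives 8.0%. The 0.60 neither shows inflation nor rules it out.
- **Pure AR(1) leaves out measurement noise.** This stands. Saliva is suctioned for about 20 seconds, and the Protocol (Generation of a Saliva Biobank) reports a 10% amplification failure rate, so independent noise is likely. With 30-50% noise the excess is at most about 1.5 percentage points. The noise shares are themselves assumptions.
- **Silence is not omission.** This also stands. No R function is named, and a correction may have been applied without being written down. A reader might infer that uncorrected degrees of freedom were used; the text supports only that no correction is specified.
- **Sphericity need not fail badly.** A reader might infer that six samples from a maturing infant must violate it. Decay with lag is plausible, but the spacing of the six analysed samples is not stated, and the size of any departure is unknown.

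None of this removes the gap: the SAP provides for covariance in the secondary models and not in the primary analysis.

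**Conclusion.** The point holds in conditional form. The SAP specifies no protection against non-sphericity for its primary within-subject tests. If none was applied, and at an assumed nominal 5%, those tests run at about 5% under a common correlation, about 5-6.5% under decaying correlation with 30-50% independent noise, and about 6-10% under pure AR(1) of 0.5-0.95.

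It would be tempting to conclude that the primary tests do run at 6-10%. The documents do not support that: they give no deltaCT covariance, no alpha, no sample spacing and no R function. Only tests involving time are affected; the between-group main effect of treatment is not. It is worth correcting because these tests carry the primary aim and an established remedy is cheap.

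**What to change.** State the significance level, and state that all within-subject tests (time and every interaction with time) use Greenhouse-Geisser or Huynh-Feldt corrected degrees of freedom. If that was already done, saying so and naming the R function closes the point.

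Alternatively, analyse deltaCT with a linear mixed model over the six time points, with an unstructured or fit-selected covariance. This would also keep infants with incomplete series, whom the present rule excludes, under a missing-at-random assumption. The secondary model cannot be copied unchanged, because it is built on four intervention phases rather than six saliva time points. Imposing AR(1) without checking its fit would replace one untested structure with another.

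The SAP is dated 3-31-24 and written in the past tense, so the real cost is confirming or re-running tests on existing data. Some p-values will become slightly larger.

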### **Saliva Collection, Processing, and Gene Expression Analysis**

*Saliva Collection:* Saliva samples will be collected from all enrolled infants on the first day prior to receiving either the SHAM or PULSED NTrainer intervention. This sample will serve as our baseline gene expression profile. Samples will then be obtained twice per week (~3 day intervals) up to the time of achievement of full oral feeds or discharge home from the hospital with either a nasogastric tube (NG) or gastrostomy tube.

Saliva samples at each site will be collected with techniques that have been optimized and validated through the [name] laboratory. Briefly, saliva samples will be collected with a 1 mL syringe, end caps removed and attached to low wall suction. Saliva will be collected for approximately 20 seconds and immediately stabilized in 500 µL of Qiagen's RNA Protect Saliva to halt gene expression changes, inhibit destructive RNases, and limit microbial overgrowth. Samples will be vortexed briefly and frozen at -20°C. Once frozen, samples are stable for up to 18 months prior to the need for total RNA extraction. Thus, samples from Nebraska and Santa Clara will be shipped once a month on ice overnight to the [name] laboratory at the Mother Infant Research Institute at Tufts Medical Center in Boston, MA for processing.

*Generation of a Saliva Biobank:* One additional saliva sample will be obtained each week from all enrolled subjects to generate a biobank repository. The rationale for this approach is twofold. First, it is possible that during shipment or processing, salivary RNA may be destroyed and not be of sufficient quality to incorporate into the study. Prior studies from this lab have demonstrated a 10% failure rate of gene amplification in saliva samples. Banking an additional sample each week from study subjects will ensure that we will limit loss of data points. Second, we anticipate that there are informative salivary biomarkers of oral feeding maturation that have yet to be identified. By generating a biobank of additional saliva samples that may be retrospectively interrogated on either a microarray gene expression platform or with RNASeq, we will have the potential to discover novel hypotheses about gene-gene interactions and/or transcriptional regulatory processes related to oral feeding in the preterm population.

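### The primary gene-expression ANOVA keeps only infants measured at all six timepoints, which discards valid randomised data and lets inclusion depend on events after randomisation

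*SAP*

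**What the plan says.** The SAP, under Primary Outcome: Gene Expression, gives the aim: "The primary goal of this study was to assess and compare differences in gene expression patterns over time between groups". Six target genes are measured at six timepoints and analysed as deltaCT by one-way and two-way ANOVA. Because measurements repeat within an infant, the repeated-measures form is used, and "subject for which all time points were not measured were excluded from the analysis". The SAP states no missing-data assumption, no sensitivity analysis, no count of excluded infants and no breakdown of exclusions by arm.

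Two routes to a missing timepoint appear in the documents.

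- **Laboratory failure.** The protocol's saliva section says: "Prior studies from this lab have demonstrated a 10% failure rate of gene amplification in saliva samples". It also provides a safeguard: "Banking an additional sample each week from study subjects will ensure that we will limit loss of data points". The SAP does not say whether banked samples were used to replace failures.
- **End of sampling.** The protocol takes routine samples twice a week "up to the time of achievement of full oral feeds or discharge home from the hospital" with a feeding tube. The SAP describes collection "beginning with the initiation of therapy through the learning process of oral feeding or to transfer to an outlying hospital". The protocol's outcome figure lists transition to full oral feeding as a secondary outcome.

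Under Secondary Outcomes, the SAP uses linear mixed models for the non-nutritive suck (NNS) measures and percent oral intake (%PO), with no complete-case restriction.

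**The concern.** The trial randomises infants and its primary aim is a between-arm comparison, yet that comparison is made only in infants with a complete series. An infant with five valid samples contributes nothing. Repeated measurement is a reason to model within-infant correlation. It is not a reason to delete incomplete infants, and the same SAP models that correlation without deletion for its secondary outcomes.

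Precision is certainly at stake as soon as any sample is missing. The make-up of the compared groups may be at stake too. Full oral feeds, discharge and transfer all follow randomisation, and the first is something the intervention is meant to influence. A banked sample cannot fill a timepoint that falls after sampling has ended.

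**Working it through.** **The plan's own sample size.** The SAP's 110 infants for 80% power (f = 0.10, correlation 0.60) stands under Secondary Outcomes. Take noncentrality f²·N·m/(1 − ρ), with alpha 0.05 and sphericity assumed. Four measures, matching the four intervention phases, need N = 111, which agrees with 110 to within one infant. Six measures need N = 87. The stated figure is therefore not a power statement for the six-timepoint gene analysis, and it is used below only as a scale.

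**Inputs.**
- 114 infants, from the SAP's Secondary Outcomes section. No number is given for the gene analysis, so this is an assumption.
- 10% failure, from the protocol's saliva section, read as failure of a whole sample. The text could also mean failure per gene, so this too is an assumption.
- Six timepoints, from the SAP, with one candidate routine sample for each unless stated.
- Clustering of failures within infants: assumed ICC of 0 to 0.5.

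**Chance of a complete series.**
- Own backup for each timepoint: a timepoint is lost with probability 0.1 × 0.1 = 0.01, so 0.99⁶ = 0.941.
- One weekly backup shared by two routine samples: (0.81 + 0.18 × 0.9)³ = 0.972³ = 0.918.
- Backup fails 25% of the time when the routine sample failed (assumption): (1 − 0.025)⁶ = 0.859.
- No replacement, independent failures: 0.9⁶ = 0.531.
- No replacement, clustered failures (beta-binomial): the product over j = 0 to 5 of (b + j)/(a + b + j), with a + b = 1/ICC − 1 and a/(a + b) = 0.10. At ICC 0.5, a = 0.1 and b = 0.9, giving 559.1/720 = 0.777. At ICC 0.1 it is 0.606.

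**Standard error.** The contrast is the change from the first to the sixth timepoint, compared between arms. For the mixed model, the generalised least squares information was summed over all 64 missingness patterns, weighted by their probabilities. For the ANOVA, only the complete pattern counts. Compound symmetry was assumed with correlation 0.3-0.8, and failure was taken as unrelated to expression. The ratio hardly varies over that range of correlation.

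| Scenario | Complete | Kept of 114 | Lost | SE ratio, ANOVA to mixed model |
|---|---|---|---|---|
| Own backup per timepoint | 0.941 | 107 | 6% | 1.02 |
| Shared weekly backup | 0.918 | 105 | 8% | 1.03 |
| Backup fails 25% | 0.859 | 98 | 14% | 1.06 |
| None, ICC 0.5 | 0.777 | 89 | 22% | 1.07 |
| None, ICC 0.1 | 0.606 | 69 | 39% | 1.21 |
| None, independent | 0.531 | 61 | 47% | 1.29 |

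**Valid samples discarded without replacement.** 114 × 6 × 0.9 = 616 samples are valid. The ANOVA drops 252 (41%) with independent failures, 201 (33%) at ICC 0.1 and 84 (14%) at ICC 0.5.

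**Spare routine samples.** Two a week over the four intervention weeks gives eight. The chance that at least six are valid is 0.962 with independent failures, 0.915 at ICC 0.1 and 0.875 at ICC 0.5, so 4-12% of infants are lost.

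**Power as a scale.** With f = 0.10, correlation 0.60, six measures and two arms, group-by-time power is 0.91 at 114 infants, 0.85 at 98, 0.81 at 89, 0.69 at 69 and 0.62 at 61. It falls below 80% once more than 27 of 114 (24%) are excluded.

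**When the timepoints fall.** If they are the first six samples and therapy starts at exactly 30 weeks, five intervals of 3-3.5 days span 15-17.5 days and end at about 32.1-32.5 weeks. The SAP's description of collection through the learning of oral feeding also allows a much later schedule.

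**The case against.** The strongest reply is that the loss may be small. The protocol banks an extra weekly sample for this very purpose, and sampling that continues into oral feeding would usually yield more than six routine samples. In every scenario that uses backup or spare samples, the loss is 4-14% of infants, which is below the 24% at which the illustrative power drops under 80%. That stands. The no-replacement rows run against the protocol's stated purpose and should not be read as the expected result. They remain possible only because the SAP is silent on replacement.

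A second reply is that bias is not shown. That also stands. A reader might infer from the stopping rule that the arm comparison is biased. That would need late timepoints, feeding time that differs by arm, and expression that tracks feeding maturity, and the documents give no figures for any of these. The opposite inference, that bias is negligible if the first six samples were used, is not supported either. The protocol's criteria for starting therapy can delay the first sample, and transfer can end sampling at any age.

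A third reply is that the SAP, dated 3-31-24, is written in the past tense, so replacing the primary model now is a post hoc change. That is a real cost and belongs in the fix. It does not restore the discarded data.

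**Conclusion.** The concern holds as a weakness of the stated method that should be fixed. The complete-case rule is explicit, it discards valid randomised data whenever a sample is missing, and it makes inclusion capable of depending on post-randomisation events.

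The size is illustrative and rests on 114 infants and 10% whole-sample failure:

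- 6-14% of infants lost and a 2-6% larger standard error if banked samples replace failures;
- 4-12% lost if any six valid of eight routine samples suffice;
- 22-47% lost and a 7-29% larger standard error if nothing replaces failures, with 47% an upper extreme.

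These figures cover failed samples only. Loss from the end of sampling would add to them by an amount that the documents do not allow to be estimated. They support neither a claim that about half the infants were lost, nor that the primary comparison is biased, nor that it is underpowered.

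**What to change.** Analyse deltaCT with a linear mixed model containing arm, time and arm-by-time, with a within-infant covariance structure, in all randomised infants with any valid sample. The SAP already uses this approach for the NNS measures and %PO. Report it beside the complete-case ANOVA, label it post hoc, show both results, and base the between-arm conclusion on the all-available-data model.

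Add to the SAP or report:

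- a definition of the six timepoints (by postconceptional age, study day or feeding milestone);
- whether banked samples replaced failed ones;
- a table of exclusions by arm and reason: failed sample, full oral feeds, tube-fed discharge, transfer.

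The cost is some wording, a short table and a re-run in software already in use, with no new data. The downsides are a post hoc change of model and reliance on missing at random. The protocol's section on initial gene expression analyses notes that genes were previously informative as present or absent, so a target-gene non-detect may itself reflect low expression. The mixed model does not fix that. It may also leave selection bias if the timepoints run late, and it extrapolates beyond full oral feeds, where sampling stops by design.
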